The study is descriptive and thus no formal statistical analysis plan has been performed. The number of subjects chosen (n=50) is based on a sample size believed to have sufficient power to reassure clinicians that tedizolid is safe, tolerable, and efficacious for the treatment of native bone and hardware-associated bone and joint infection.

Of note, confidence intervals for safety and efficacy will be calculated. Confidence intervals for outcomes of low incidence (e.g., thrombocytopenia) will be approximately +/-3 - 7%. E.g., assuming n=50 subjects, a low incidence outcome with a probability of 2.5% will have 95% confidence intervals of <0.1%-6.8%. Outcomes with probabilities farther from 0% or 100% will have wider confidence intervals. For example, we anticipate cure rate will be 80%, in which assuming n=50, 95% confidence intervals will be 69%-91%.

Provide a power analysis.

Confidence intervals for safety and efficacy will be calculated. Confidence intervals for outcomes of low incidence (e.g., thrombocytopenia) will be approximately +/-3 - 7%. E.g., assuming n=50 subjects, a low incidence outcome with a probability of 2.5% will have 95% confidence intervals of <0.1%-6.8%. Outcomes with probabilities farther from 0% or 100% will have wider confidence intervals. For example, we anticipate cure rate will be 80%, in which assuming n=50, 95% confidence intervals will be 69%-91%.

Describe the steps that will be taken to secure the data (e.g., training, authorization of access, password protection, encryption, physical controls, certificates of confidentiality, and separation of identifiers and data) during storage, use, and transmission.

All source documents and specimens will be coded meaning these items will be labeled the subjects Study ID number and will include dates (case report forms) rather than his/her name and/or date of birth. We will maintain a separate password-protected key list/log (electronic file) linking each subject to their Study ID and a hardcopy will be maintained separate from individual subject files in a separate locked filing cabinet. Access to study computers and files will be limited to study personnel. Human research records including Informed Consent Forms

PROTOCOL TITLE: *Tolerability, Safety, and Efficacy of Tedizolid as Oral Treatment for Bone and Joint Infection*

Revised: 8/10/18 Version 1.6

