The study staff and study investigators will review the data.

Study staff will review all recorded data at regular monthly intervals with the primary investigator, [name]. If [name] is not available, the co-investigator, [name], will review the monthly data.

The Data Safety Monitor ([name]) will review safety data including labs, vital signs, results of peripheral neuropathy scales, and all reported adverse events, side effects, complications, or other patient feedback. This review will occur on a quarterly basis, with the first review happening after either three months or after 10 patients have been enrolled, whichever comes first.

The frequency or periodicity of review of cumulative data.

Cumulative safety data will be reviewed by the study staff and study investigators as it becomes available.

The statistical tests for analyzing the safety data to determine whether harm is occurring.

We will perform reviews once per quarter of the cumulative side effects. A summary of these safety data including labs, vital signs, results of peripheral neuropathy scales, and all reported adverse events, side effects, complications, or other patient feedback will be shared with the study's Data Safety Monitor, [name]. If there is a statistically significant side effects, the Principal Investigator and/or the Data and Safety Monitor for the study, will consider reporting this to the IRB if the side effects are felt to put subjects at harm. Any serious adverse events that pose a risk to the subject or others and are deemed unexpected and possibly or probably related to the study will be reported to the IRB within 24 hours of the study staff being aware of this event, in accordance with HRP-214.

- *Any conditions that trigger an immediate suspension of the research.*

If, in the belief of the Principal Investigator or the Data and Safety Monitor, there are events that put subjects at undue risk, due to either cumulative or individual events outlined above, the study will be immediately suspended.

I) Withdrawal of Subjects*

Describe anticipated circumstances under which subjects will be withdrawn from the research without their consent.

Subjects will be withdrawn from the study without their consent if the principal investigator determines this is necessary to protect the safety of the subject.

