Phase 1 studies conducted in healthy adults exposed to tedizolid (200 mg oral/intravenous once daily) for 21 days showed a possible dose and duration effect on hematologic parameters beyond 6 days of treatment.

Peripheral and optic neuropathy have been described in patients treated with another member of the oxazolidinone class for longer than 28 days. In Phase 3 ABSSI trials, reported adverse reactions for peripheral neuropathy and optic nerve disorders were similar between both treatment arms (peripheral neuropathy 1.2% vs. 0.6% for tedizolid phosphate and linezolid, respectively; optic nerve disorders 3% vs. 0.2%, respectively). No data are available for patients exposed to tedizolid for longer than 6 days.

If applicable, indicate which procedures may have risks to the subjects that are currently unforeseeable.

Use of prolonged tedizolid treatment (4-12 weeks) has not yet been studied or approved by the FDA, which may pose currently unforeseeable risks. However, tedizolid has a favorable adverse event profile and low thrombocytopenia rates compared to linezolid which is approved by the FDA for prolonged antibiotic therapy. Additionally, at FDA-approved doses, tedizolid has

PROTOCOL TITLE: *Tolerability, Safety, and Efficacy of Tedizolid as Oral Treatment for Bone and Joint Infection*

Revised: 8/10/18 Version 1.6

hematologic side effects similar to that of placebo. Additionally, unlike linezolid, interactions with SSRIs appear unlikely. Drug-mitochondrial binding, which is believed to be the mechanism to which mid- and long-term toxicities of linezolid such as neuropathy are acquired, is not seen with tedizolid, suggesting that the side effects associated with long-term therapy of linezolid may not be found with tedizolid. Tedizolid will be used in this research to treat bone and joint infection in patients who need prolonged antibiotic treatment for 4-12 weeks.

Despite these promising initial results, there still may be currently unforeseeable risks. For this reason, Drs. [name] and [name] will closely monitor subject data in monthly reviews, and a Data Safety Monitor ([name]) will review all safety data (including labs, vital signs, results of peripheral neuropathy scales, and all reported adverse events, side effects, complications, or other patient feedback) every three months or after 10 patients have been enrolled, whichever comes first.

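### Considering an IRB report of cumulative side effects depends first on statistical significance, which this single-arm descriptive plan never defines (minor)

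*Combined protocol and SAP*

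**What the plan says.** Section 9(k), on monitoring the data, answers a template prompt: "The statistical tests for analyzing the safety data to determine whether harm is occurring". The answer describes quarterly reviews and a summary for the Data Safety Monitor, and names no test. It continues: "If there is a statistically significant side effects, the Principal Investigator and/or the Data and Safety Monitor for the study, will consider reporting this". The report would go to the IRB, and a second condition is attached: "if the side effects are felt to put subjects at harm". Section 10, Risks to Subjects, repeats the sentence.

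The surrounding text gives the condition no content:

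- Section 9(g) describes an open-label, non-comparative trial.
- Section 9(i) says "The study is descriptive and thus no formal statistical analysis plan has been performed". It adds "Of note, confidence intervals for safety and efficacy will be calculated", but does not link those intervals to the reporting sentence.
- Section 10 lists adverse-reaction and laboratory rates from 6-day courses in skin-infection trials. It offers them as risks, not as benchmarks.
- Section 10 also says of 21-day studies in healthy adults that they "showed a possible dose and duration effect on hematologic parameters beyond 6 days of treatment", and of patients: "No data are available for patients exposed to tedizolid for longer than 6 days". Treatment in this trial lasts 4 to 12 weeks.

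**The concern.** The sentence stacks two conditions: significance first, then a judgement of harm. The judgement can be made by the people named. Significance cannot be settled from the plan, because nothing says what is tested, against what, or at what level. Two careful readers of the same quarterly summary could disagree on whether the condition is met.

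At stake is a narrow class of findings: non-serious or expected side effects that accumulate, are felt to harm subjects, and fall short of the undue-risk standard for suspension. Tolerability is the primary endpoint (section 9(f)), so such findings are what this study is likely to produce. A literal reader could hold back from considering a report of them because an undefined statistical hurdle had not been cleared.

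**Working it through.** **1. The plan's own figures.** The only inferential numbers are two 95% intervals at n=50 in section 9(i). Both match the normal approximation p ± 1.96·√(p(1−p)/50):

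- p=0.025: 0.025 ± 1.96 × 0.02208 = −1.8% to 6.8% (printed as <0.1% to 6.8%).
- p=0.80: 0.80 ± 1.96 × 0.05657 = 68.9% to 91.1% (printed as 69% to 91%).

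They describe precision. Neither sets a threshold for harm.

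**2. How far the condition moves with the missing choices.** Take low platelets in 50 patients and a one-sided exact binomial test. The 2.3% is the 6-day rate in Table 1 of section 10. The other reference rates and all alphas are assumptions.

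| Reference rate | Events needed, alpha 0.05 | Events needed, alpha 0.01 |
|---|---|---|
| 2.3% | 4 | 5 |
| 5% | 6 | 8 |
| 10% | 10 | 11 |
| 20% | 16 | 18 |

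The count that would be significant runs from 4 to 18 of 50, and the documents do not choose among these.

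**3. What the condition could screen out at the first review.** Section 9(k) sets that review at three months or 10 patients, whichever comes first. Take 10 patients, reference 2.3%, one-sided alpha 0.05 (assumed).

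- One event: p = 1 − 0.977^10 = 0.208, not significant.
- Two events: p = 0.021, significant. So two events are needed.
- If the true rate is 10% (assumed):
  - at least one event: 1 − 0.9^10 = 65.1%;
  - exactly one event: 10 × 0.1 × 0.9^9 = 38.7%;
  - two or more: 65.1% − 38.7% = 26.4%.

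Thus up to 38.7% of such reviews would show an event that does not meet the condition. This is an upper bound on what the wording could remove, because the event must also be felt to put subjects at harm.

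**4. Interval method, for the fix.** With 0 events in 10, the normal approximation gives 0% to 0%. The exact upper limit is 1 − 0.025^(1/10) = 30.8%. Exact intervals at n=50 are 0.05% to 10.6% for 1/50 and 66.3% to 90.0% for 40/50.

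**The case against.** **A test is possible in one arm.** A reader might infer that significance can never be evaluated here. The documents do not support that. A baseline CBC and chemistry panel, the same tests at each follow-up visit, and surveys at enrolment and follow-up are all collected (sections 9(b) and 9(g)). Change from each patient's own baseline could be tested without an external rate. This objection stands: the condition is unspecified, not impossible. The plan does not say that such a test is meant.

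**The sentence says if, not only if.** Nothing forbids considering a report without significance. This also stands, so the screening effect is a literal reading and not a stated prohibition. But a first condition that adds nothing should not be there, and the template prompt about statistical tests invites the literal reading.

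**Stronger routes exist.** A reader might infer that serious harm could go unreported or the trial run on unchecked. The documents say otherwise. Unexpected, related serious events that pose a risk go to the IRB within 24 hours. Suspension rests on the belief of the investigator or monitor and covers cumulative as well as individual events. Withdrawal is available for cytopenias, liver abnormalities, neuropathy symptoms and gastrointestinal intolerance. Weekly blood counts continue until myelosuppression resolves. The 24-hour route cites HRP-214, which is not among the documents, so whether that policy also covers the remaining class is unknown.

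**The illustration uses a doubtful reference.** It tests against a 6-day rate that section 10 gives reason not to carry to 4 to 12 weeks. That is fair. The 39% is not an estimate of missed harm, and part of it reflects only how little 10 patients can show.

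**Conclusion.** The point holds as a minor one. Sections 9(k) and 10 put an undefined significance condition ahead of a harm judgement that could work alone. This rests on the text and needs no assumed rate. Its reach is limited to considering an IRB report of cumulative harm that is non-serious or expected and short of undue risk. The 39% is an upper bound under an assumed test, alpha, reference rate and true rate.

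**What to change.** 1. In sections 9(k) and 10, delete the opening clause about significance and let the clause "if the side effects are felt to put subjects at harm" stand as the only condition for considering an IRB report.
2. Answer the prompt on statistical tests in section 9(k) directly: no hypothesis test is used, and the existing quarterly summary shows event counts with the safety confidence intervals already planned in section 9(i).
3. Preferably specify exact intervals, since the normal approximation fails at zero events. If so, restate the section 9(i) examples, which appear under both the analysis plan and the power analysis. Because 2.5% of 50 is 1.25 events and cannot be observed, use 1/50 (0.05% to 10.6%) and 40/50 (66.3% to 90.0%). The stated half-width of about 3 to 7 points for low-incidence outcomes then needs rewording too: for 1/50 the upper limit lies 10.6 − 2.0 = 8.6 points above the estimate.

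Leave the rules for serious-event reporting, suspension and withdrawal as they are.

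The cost is one clause deleted in two places, one or two sentences added, minor tabulation, possibly a few more IRB reports, and slightly less favourable stated precision for rare events. The decision remains one of judgement, and reviewers may still differ.

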- *Where and how data or specimens will be stored locally?*

All source documents/data will be maintained in Room 228 of Building RB-2 in a locked file cabinet in a locked office. Data will be stored digitally via the REDCap system, an online secure database. Specimens will be stored in a locked laboratory in a secure building (room 235, RB-3).

- *How long will the data or specimens will be stored locally?*

All PHI or other identifying information, including the subject log linking the subject name and study ID will be stored for at least 3 years after the completion of the study. De-identified data and specimens will be stored for 25 years after the completion of the study.

Who will have access to the data or specimens locally?

Only persons listed on the Delegation of Authority Log will have access to the data locally.

Who is responsible for receipt or transmission of the data or specimens locally?

The Principal Investigator and main study coordinator(s) are responsible for receipt or transmission of the data. The CTRC/CSTI is responsible for transmission of the specimens to Quest Diagnostics. The specimens will be transported per Quest Diagnostics' and the CTRU/CTSI's standards for transporting blood samples, as the CTRU/CTSI sends all blood samples collected at follow up visits to Quest Diagnostics for processing.

How data and specimens will be transported locally?

Data will be recorded on paper, using a Case Report Form Binder (See Data Collection Fields, V1.0). Source documents will be stored in a locked office on a locked floor of a secure building in Room 228 of Building RB-2.

k) Provisions to Monitor the Data to Ensure the Safety of subjects*

This is required when Human Research involves more than minimal risk to subjects.

Describe the plans to periodically evaluate the data collected regarding both harms and benefits to determine whether subjects remain safe.

PROTOCOL TITLE: *Tolerability, Safety, and Efficacy of Tedizolid as Oral Treatment for Bone and Joint Infection*

Revised: 8/10/18 Version 1.6

We will review safety/tolerability summary data monthly. On a quarterly basis, we will provide the reports to the Data and Safety Monitor for the study, [name].

The plan might include establishing a data monitoring committee and a plan for reporting data monitoring committee findings to the IRB and the sponsor.

Describe:

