- *The plan to periodically evaluate the data collected regarding both harms and benefits to determine whether subjects remain safe.*

Study staff will review all recorded data at regular monthly intervals with the primary investigator, [name]. If [name] is not available, the co-investigator, [name], will review the monthly data.

The Data Safety Monitor ([name]) will review safety data including labs, vital signs, results of peripheral neuropathy scales, and all reported adverse events, side effects, complications, or other patient feedback. This review will occur on a quarterly basis, with the first review happening after either three months or after 10 patients have been enrolled, whichever comes first.

- *What data are reviewed, including safety data, untoward events, and efficacy data.*

All reported adverse events, side effects, or complications will be reviewed.

How the safety information will be collected (e.g., with case report forms, at study visits, by telephone calls with participants).

Safety information will be recorded by patients in the medication diary, which will be given to study staff and reviewed (See attached Medication Diary, V1.0). Additionally, study staff will inquire with patients at each visit (week 1, week 2, week 3, week 4, week 5, week 6 (optional), week 7(optional), week 8 (optional), week 9 (optional), week 10 (optional), week 11 (optional), week 12, and week 13 (optional) and the phone call at 3 months after end of antibiotic treatment) about safety information and any experienced side effects or adverse events. This data will be recorded on the Data Collection Form by study staff (See Data Collection Fields, V1.0) and entered into REDCap, an online secure database.

The frequency of data collection, including when safety data collection starts.

Data collection, which also includes safety data collection (all reported adverse events, side effects, or complications) will begin at the initial visit/time of screening and enrollment and continue at each follow up visit (week 1, week 2, week 3, week 4, week 5, week 6 (optional), week 7(optional), week 8 (optional), week 9 (optional), week 10 (optional), week 11 (optional), week 12, week 13 (optional) and the phone call at 3 months after end of antibiotic treatment).

Who will review the data.

PROTOCOL TITLE: *Tolerability, Safety, and Efficacy of Tedizolid as Oral Treatment for Bone and Joint Infection*

Revised: 8/10/18 Version 1.6

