Additionally, subjects may be withdrawn in the following circumstances development of significant cytopenias and liver function abnormalities, symptoms of neuropathy, gastrointestinal intolerance, or, in the opinion of the investigator, any new severe signs or symptoms that may be related to the study drug.

PROTOCOL TITLE: *Tolerability, Safety, and Efficacy of Tedizolid as Oral Treatment for Bone and Joint Infection*

Revised: 8/10/18 Version 1.6

If a subject becomes pregnant during the study, they will be discontinued from the study drug. Study staff will follow and collect data on the course of the pregnancy and the health of the child for at least 6-8 weeks after delivery.

Describe any procedures for orderly termination.

Termination of the study will occur based on the primary investigators judgment. Subjects will be provided referrals for their medical conditions, if needed.

Describe procedures that will be followed when subjects withdraw from the research, including partial withdrawal from procedures with continued data collection.

Subjects who withdraw from the study will be asked to notify the study team. No further visits will be required. Additionally, if a subject withdraws from the study, a member of the study team will contact their primary treatment physician and/or infectious disease consultant to ensure that the patient is given antibiotic therapy immediately upon discontinuation of study drug.

10) Risks to Subjects*

List the reasonably foreseeable risks, discomforts, hazards, or inconveniences to the subjects related the subjects' participation in the research. Include as may be useful for the HSC's consideration, describe the probability, magnitude, duration, and reversibility of the risks. Consider physical, psychological, social, legal, and economic risks.

According to the package insert for tedizolid (Sivextro), adverse reactions were evaluated for 1050 patients treated with tedizolid (200 mg oral/intravenous once daily for 6 days) in two Phase 2 and two Phase 3 ABSSSI (acute bacterial skin and soft structure infection) clinical trials. The median age of patients treated with tedizolid (200 mg oral/intravenous once daily for 6 days) in the Phase 2 and Phase 3 ABSSSI trials was 42 years, ranging between 17 and 86 years old. Patients treated with tedizolid (200 mg oral/intravenous once daily for 6 days) were predominantly male (65%) and white (82%).

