Serious adverse reactions occurred in 12/662 (1.8%) of patients treated with tedizolid (200 mg oral/intravenous once daily for 6 days). Tedizolid (200 mg oral/intravenous once daily for 6 days) was discontinued due to an adverse reaction in 3/662 (0.5%) of patients.

The most common adverse reactions in patients treated with tedizolid (200 mg oral/intravenous once daily for 6 days) were nausea (8%), headache (6%), diarrhea (4%), vomiting (3%), and dizziness (2%). The median time of onset of adverse reactions was 5 days for both tedizolid(200 mg oral/intravenous once daily for 6 days) with 12% occurring on the second day of treatment.

The following selected adverse reactions were reported in tedizolid-treated patients at a rate of less than 2% in the pooled Phase 3 ABSSSI clinical trials:

Blood and Lymphatic System Disorders: anemia

Cardiovascular: palpitations, tachycardia

Eye Disorders: asthenopia, vision blurred, visual impairment, vitreous floaters

General Disorders and Administration Site Conditions: infusion-related reactions

PROTOCOL TITLE: *Tolerability, Safety, and Efficacy of Tedizolid as Oral Treatment for Bone and Joint Infection*

Revised: 8/10/18 Version 1.6

Immune System Disorders: drug hypersensitivity

Infections and Infestations: *Clostridium difficile* colitis, oral candidiasis, vulvovaginal mycotic infection

Investigations: hepatic transaminases increased, white blood cell count decreased

Nervous System Disorders: hypoesthesia, paresthesia, VIIth nerve paralysis

Psychiatric Disorders: insomnia

Skin and Subcutaneous Tissue Disorders: pruritus, urticaria, dermatitis

Vascular Disorders: flushing, hypertension

Additionally, hematology laboratory abnormalities that were determined to be potentially clinically significant in the pooled Phase 3 ABSSI clinical trials are provided in Table 1.

Table 1: Potentially Clinically Significant Lowest Laboratory Values*† in the Pooled Phase 3 ABSSI Clinical Trials

Laboratory Assay	Tedizolid (200 mg oral/intravenous once daily for 6 days) (N=618) ‡
Hemoglobin (<10.1 g/dL [M]) (<9 g/dL [F])	3.1%
Platelet count (<112 × 10 ³ /mm ³)	2.3%
Absolute neutrophil count (<0.8 × 10 ³ /mm ³)	0.5%

M = male; F = female

* <75% (<50% for absolute neutrophil count) of lower limit of normal (LLN) for values normal at baseline

† Represents lowest abnormal post-baseline value through the last dose of active drug

‡ Number of patients with non-missing laboratory values

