If there is a statistically significant side effects, the Principal Investigator and/or the Data and Safety Monitor for the study, will consider reporting this to the IRB if the side effects are felt to put subjects at harm. Any serious adverse events that pose a risk to the subject or others and are deemed unexpected and possibly or probably related to the study will be reported to the IRB within 24 hours of the study staff being aware of this event, in accordance with HRP-214.

Additionally, if in the belief of the Principal Investigator or the Data and Safety Monitor, there are events that put subjects at undue risk, due to either cumulative or individual events outlined above, the study will be immediately suspended.

If applicable, indicate which procedures may have risks to an embryo or fetus should the subject be or become pregnant.

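### The protocol's only statistical harm trigger names no event, reference rate, test or alpha, and in the text supplied no toxicity count obliges a monitor review or an enrolment hold

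*Combined protocol and SAP*

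**What the plan says.** Section 9) k) answers the template's question on statistical tests for harm with a quarterly cumulative review and one conditional sentence: "If there is a statistically significant side effects, the Principal Investigator and/or the Data and Safety Monitor for the study, will consider reporting this". Section 10 repeats it. The action carries a second condition of judgement: the investigator or monitor "will consider reporting this to the IRB if the side effects are felt to put subjects at harm". Section 9) i) adds: "The study is descriptive and thus no formal statistical analysis plan has been performed".

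Other safeguards do not depend on that sentence:
- Investigator review: "We will review safety/tolerability summary data monthly". Cumulative data are also looked at as they arrive.
- Data and Safety Monitor: quarterly, "with the first review happening after either three months or after 10 patients have been enrolled, whichever comes first". That trigger counts time or enrolment, not toxicity.
- Serious events that pose a risk, are unexpected and are possibly or probably related go to the IRB within 24 hours.
- If the investigator or the monitor believes subjects are at undue risk, "due to either cumulative or individual events outlined above, the study will be immediately suspended".
- Blood counts are taken at every follow-up visit, and weekly until any myelosuppression resolves (section 9) g)).
- Individual subjects may be withdrawn for "development of significant cytopenias and liver function abnormalities, symptoms of neuropathy, gastrointestinal intolerance" and other severe findings (section 9), Withdrawal of Subjects).

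**The concern.** Tolerability is the primary endpoint and safety the secondary. Section 10 states that no patient data exist beyond 6 days of dosing, and that 21-day Phase 1 data in healthy adults showed a possible dose and duration effect on blood counts. This trial doses for 4 to 12 weeks.

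A single-arm rate can be tested, but only against a fixed reference. The protocol prints several candidates from the short-course skin-infection trials and links none of them to the trigger. They may also be too low a benchmark for a much longer course. Whoever applies the sentence must therefore choose the event, reference and alpha after seeing the data. Two careful readers can reach opposite answers on the same counts, and the chance that the trigger acts at a given toxicity rate cannot be stated. No number of toxicities fills the gap by obliging an unscheduled review or a pause.

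**Working it through.** **1. The plan's own figures.** The only statistical figures given are two confidence intervals at n = 50 (section 9) i)). With p ± 1.96·√(p(1−p)/50):
- 2.5%: ±4.3 points, or −1.8% to 6.8%. The plan prints the lower limit as <0.1%.
- 80%: ±11.1 points, or 68.9% to 91.1%. The plan gives 69%-91%.

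Both reproduce. Neither concerns the trigger, for which there is no figure to reproduce.

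**2. What the trigger could mean.** Section 10 reports that in 6-day use tedizolid "was discontinued due to an adverse reaction in 3/662 (0.5%) of patients". It also prints low platelets in 2.3%, peripheral neuropathy in 1.2% and nausea in 8%. Taking each as the reference, the exact upper tail P(X ≥ r | n, p0) gives:
- Drug stops, p0 = 3/662, n = 10: r = 1 gives 1 − (1 − 3/662)^10 = 0.044; r = 2 gives 0.0009. One stop is significant at 5%; two are needed at 2.5%.
- Low platelets, p0 = 2.3%, n = 10: r = 1 gives 0.208; r = 2 gives 0.021.
- Low platelets, 4 of 50: 0.028 against 2.3%, but 0.240 against an assumed 5%.

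Smallest count significant at one-sided 5%:

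| Event (reference) | n = 10 | n = 50 |
|---|---|---|
| Drug stop (0.5%) | 1 | 2 |
| Neuropathy (1.2%) | 2 | 3 |
| Low platelets (2.3%) | 2 | 4 |
| Nausea (8%) | 3 | 8 |

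If the true stop rate were 10% (assumed) and 10 outcomes were known, the stop reading would be met with probability 1 − 0.9^10 = 65% at alpha 5%, and P(X ≥ 2) = 26% at alpha 2.5%.

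**3. What a defined rule would do.** Planned accrual is 55/16 = 3.4 subjects a month. As an illustration, take a tolerated stop rate p0, a Beta(p0, 1 − p0) prior, and a hold when P(rate > p0 | data) > 0.95, from 5 dosed subjects on. At an assumed p0 = 10% the boundary is 3/5, 4/10, 5/20, 7/30, 8/40, 10/50. I simulated 55 entries over 16 months, a monthly tally, all dosed subjects as denominator, and onset spread evenly over 12 weeks (assumed):

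| True stop rate | Boundary ever crossed | Crossed before last entry | Mean enrolled at crossing or completion |
|---|---|---|---|
| 10% | 7-8% | 6% | 53-54 |
| 15% | 37% | – | – |
| 20% | 73% | 61% | 39 |
| 30% | 99% | 96% | 24 |

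If outcomes were immediate and the tally continuous, exact recursion gives crossing in 14.6%, 79.2% and 99.1% of studies at 10%, 20% and 30%. Other choices: p0 = 5% gives 6-7% at a true 5% and over 99% at 30%; p0 = 15% gives about 6% at a true 15% and about 85% at 30%.

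**The case against.** The strongest reply is that little turns on the phrase. It gates one discretionary act, considering an IRB report, and does not gate suspension, which is mandatory once the investigator or the monitor believes subjects are at undue risk. In an unblinded, descriptive, single-site pilot with monthly review, judgement-based monitoring can be acceptable, and nothing in the document requires a numeric boundary. All of this stands, and it limits the size of the point. What remains is that the protocol itself offers statistical significance as its harm test, and that test cannot be run.

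The 65% against 26% contrast is a chosen example. One stop is significant at 5% only up to 11 subjects (p = 0.049) and not at 12 (p = 0.053). It also assumes 10 known outcomes, whereas the monitor's first review counts 10 enrolments. It shows ambiguity, not harm to subjects.

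A count of drug stops has limits too. Stopping is itself a clinical judgement. Pooling gastrointestinal stops with neuropathy would let four neuropathy stops in 20 pass under a 5/20 limit, so neuropathy needs its own lower limit. At 3.4 entries a month, a rule starting at five subjects will usually be silent at the first tally. No gain over an attentive investigator reading the same data is demonstrated.

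A reader might infer that the trial has no effective safety monitoring, or that a significance test must be passed before the study can be stopped. The document supports neither: the reviews are scheduled, and the suspension and 24-hour reporting clauses carry no statistical condition.

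**Conclusion.** The concern holds in limited form. The trigger is unusable as written, because event, reference, test and alpha would all have to be chosen after seeing the data. In the text supplied, no toxicity count obliges a monitor review or an enrolment hold. The institutional procedure cited for IRB reporting (HRP-214) and the attached forms were not available, so that second statement covers the visible text only.

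In size, the defect touches a reporting route rather than the suspension route. It is still worth correcting: the endpoints are tolerability and safety, the exposure is longer than any patient data the protocol cites, and the repair is small. The tail probabilities are exact given the printed references. The boundary results rest on the assumed tolerated rate, the even 12-week onset and steady accrual, and illustrate what a defined rule can do rather than prescribe a threshold.

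**What to change.** Amend section 9) k) and its repeat in section 10:

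1. In the IRB-reporting sentence, delete the words requiring statistical significance, so that any side effects felt to put subjects at harm are considered for reporting.
2. Add a count boundary. Event: study drug stopped for a toxicity listed under Withdrawal of Subjects. Denominator: all dosed subjects. Timing: the existing monthly review.
3. Count neuropathy separately under a lower boundary. As an illustration at an assumed tolerated rate of 5%, exact one-sided 0.025 at each look gives 3/10, 4/20, 5/30, 6/40, 7/50. With outcomes known at each look, this is crossed in 3.7%, 32%, 71% and 92% of studies at true rates of 5%, 10%, 15% and 20%.
4. On crossing, the existing Data and Safety Monitor makes an unscheduled review, new enrolment is held until it is done, and the crossing is reported to the IRB.
5. Keep the belief-based suspension clause. It covers toxicity that does not lead to a stop, and the first few subjects.
6. The investigator and monitor fix the tolerated rates before use and print the boundaries with their joint operating characteristics.

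Cost: one paragraph, one small table, a running tally and one extra monitor review if a boundary is crossed. The downside is a temporary hold in about 7-8% of studies when the true overall stop rate equals an assumed 10% (up to about 15% with immediate outcomes and a continuous tally), plus whatever the neuropathy limit adds.
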